### 5.2 Subject Population

Adult male and female subjects, 18 years or older, who are scheduled to undergo general inhaled anesthesia will be invited to voluntarily participate in this study.

### 5.3 Protection of Vulnerable Subjects

This study does not examine any groups of subjects that are considered to be vulnerable subjects; i.e. pregnant women/fetuses, neonates, children or minor subjects, employees/faculty, cognitively impaired, and prisoners.

### 5.4 Inclusion Criteria

Subjects, who meet all of the following inclusion criteria, may be included:

**Study Title:** Multi-site Anesthesia randomized controlled Study of End tidal control (Et Control) compared to conventional anesthesia Results (MASTER-Anesthesia Trial)  
**Study No:** 123.07-2015-GE5-0002

GE Healthcare

2. Male or female 18 years old or greater
3. Scheduled to undergo general inhaled anesthesia that can be safely exposed to 100% oxygen for up to 2 minutes during general anesthesia
4. Expected to have airway secured with laryngeal mask airway (LMA) or endotracheal tube
5. Undergoing a surgical procedure that is anticipated by the investigator to take greater than or equal to 1 hour (operative time measured from induction to cessation of general inhalation anesthetic)
6. Meets one of the American Society of Anesthesiologists (ASA) status classification system I through III:
  - a. ASA Physical Status 1 = a normal healthy patient
  - b. ASA Physical Status 2 = a patient with mild systemic disease
  - c. ASA Physical Status 3 = a patient with severe systemic disease
7. Undergoing intravenous induction
8. Able to provide written informed consent

**NOTE:** *The inclusion criterion related to the length of the surgical procedure is not related to any clinical, medical, or safety risk. Length of use or procedure length is not clinically relevant to the use of the Et Control option or Aisys CS anesthesia machine. This is solely to help ensure that sufficient amounts of data are collected related to the use of the Et Control option during the study to maximize the clinical value of each subject enrolled.*

## 5.5 Exclusion Criteria

Subjects, who meet any of the following exclusion criteria, will be excluded:

1. Have emergency medical condition requiring surgery
2. Are female subjects, who are pregnant or lactating
3. Any subject undergoing cardiac bypass surgery
4. Any subject undergoing open chest surgery

**NOTE:** *Exclusions 1 and 2 is established for ethical reasons. Exclusion criteria 3 and 4 are is to avoid long gaps of data collection and transitions on and off the anesthesia machine during surgical case. None of these exclusions are due to limitations of the device.*

## 5.6 Screening and Recruiting Subjects for Enrollment

Enrollment in the study will begin after the IDE has been approved by the FDA and the investigational site identified has received Institutional Review Board (IRB) approval.

**Study Title:** Multi-site Anesthesia randomized controlled Study of End tidal control (Et Control) compared to conventional anesthesia Results (MASTER-Anesthesia Trial)  
**Study No:** 123.07-2015-GE5-0002

GE Healthcare

### 5.6.1 Recruitment/Consent Process

Subjects will be recruited for potential enrollment in this study according to the standard procedures of the investigational site, unless otherwise specified by the Sponsor in this study protocol. Subjects will be asked to volunteer to participate in this research study.

The subject or authorized representative will be informed of the requirements of the study as well as the potential risks and benefits. They will be required to read and indicate understanding of the IRB and Sponsor-approved Informed Consent document/HIPAA Authorization. The subject will be given the opportunity to ask questions. Upon provision of written informed consent, screening procedures begin, and subject is randomized into the study.

Following enrollment, a subject will be considered enrolled (the point of enrollment) once he/she signs and dates the informed consent form (ICF). Once enrolled, the subject will be assigned a unique subject number, which will not contain information that could identify the subject (such as subject name or date of birth). The unique subject number will be used to label electronic case report forms (eCRFs) data as well as data collected in by the Aisys CS2 for the subject throughout his/her participation in the study.

[figure not shown]
**Study Title:** Multi-site Anesthesia randomized controlled Study of End tidal control (Et Control) compared to conventional anesthesia Results (MASTER-Anesthesia Trial)  
**Study No:** 123.07-2015-GES-0002

GE Healthcare

## 5.6.2 Screening

Figure 5-1 – Diagram of Study Procedures

- Notes:**
1. Subject is considered enrolled once written informed consent has been obtained. Screening procedures begins once informed consent has been obtained.
  2. Screening procedures and randomization must occur within 24 hours prior to Induction and Intubation.

Upon provision of written informed consent, subjects will be screened for enrollment in this study against the inclusion and exclusion criteria; according to the standard procedures of the investigational site, unless otherwise specified by the Sponsor in this study protocol. Screening procedures and randomization must occur within 24 hours prior to induction and intubation.

## 6. PROCEDURES FOR RESEARCH STUDY

### 6.1 Randomization and Enrollment

Subjects will be randomized at a ratio of 1:1 to either the "Investigational Et Control Arm" or the "Control Arm." Stratified randomization will be used based on Investigator, subject's pre-existing hypertension status, and subject's ASA status. Randomization sequences will be

**Study Title:** Multi-site Anesthesia randomized controlled Study of End tidal control (Et Control) compared to conventional anesthesia Results (MASTER-Anesthesia Trial)  
**Study No:** 123.07-2015-GES-0002

GE Healthcare

assigned through the IVRS/IWRS system. Subjects will be considered enrolled after providing written informed consent.

The following devices will be employed for each arm of the study:

- ♦ **Investigational Et Control Arm:** legally marketed Aisys CS anesthesia machine with investigational Et Control option
- ♦ **Control Arm:** legally marketed Aisys CS anesthesia machine without the investigational Et Control option

### 6.1.1 Investigational Et Control Arm

The subjects assigned to this group are induced and their airway secured based on each investigator's conventional intravenous induction and intubation practice. Machine log data are collected when the investigator initiates the start of anesthesia case on the Aisys CS.

The investigator will initiate Et Control after the airway is secured (intubation) and mechanical ventilation is initiated. Machine log data is collected when the investigator initiates the start of anesthesia case on the Aisys CS. Adjustments to the anesthesia machine settings, discontinuation of use of the investigational Et Control option, and changes to treatment are based upon clinician judgment for the wellbeing of the subject. This protocol does not in any way instruct the clinician to make any dosage changes or adjustments for study purposes. All dosage decisions are based on their normal clinical practice.

Aisys CS machine log data collection will end when an "end case" is confirmed on the Aisys CS at the end of the anesthesia case. Evaluable Aisys CS data ends when the patient is finally disconnected from the Aisys CS breathing system.

The clinician must continuously monitor measured inspired and end tidal oxygen and anesthetic concentrations to assess individual responses and compare to the target concentrations.

The clinician must maintain adequate ventilation to deliver appropriate oxygen and anesthetic agent to the patient. Et Control does not adjust ventilator parameters.

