## 3.4 Study Endpoints

### 3.4.1 Primary Endpoint:

- (1) Percent duration without large deviation of EtAA:

Percent duration of EtAA concentration during steady state maintained within the acceptable limit, which is defined as the greater of 5% of the steady state inhaled anesthetic agent concentration and 0.6% v/v for Desflurane (Des), 0.2% v/v for Sevoflurane (Sev), or 0.1% v/v for Isoflurane (Iso). The percent duration is the weighted average of all steady states for a subject, using the duration of steady state as the weight. It is expressed as:

**Study Title:** Multi-site Anesthesia randomized controlled Study of End tidal control (Et Control) compared to conventional anesthesia Results (MASTER-Anesthesia Trial)  
**Study No:** 123.07-2015-GE5-0002

GE Healthcare

$$PercentDuration = \frac{\sum_j \sum_i t_{ij} I_{ij}}{\sum_j T_j} \times 100\% \quad \text{where } t_{ij} \text{ is the } i^{\text{th}} \text{ duration of EtAA concentration}$$

maintained within the acceptable limit during the  $j^{\text{th}}$  steady state, and  $T_j$  is the total duration of the  $j^{\text{th}}$  steady state.  $I_{ij}$  is an indicator for whether EtAA is maintained within the acceptable limit of  $i^{\text{th}}$  duration in  $j^{\text{th}}$  steady state, which is

$$I = \begin{cases} 1 & \begin{array}{l} \text{if Desflurane and } \Delta EtAA \leq \max(0.6\%, 5\%X \text{ steady state EtAA}) \\ \text{if Sevoflurane and } \Delta EtAA \leq \max(0.2\%, 5\%X \text{ steady state EtAA}) \\ \text{if Isoflurane and } \Delta EtAA \leq \max(0.1\%, 5\%X \text{ steady state EtAA}) \end{array} \\ 0 & \text{otherwise} \end{cases}$$

$\Delta EtAA$  is the absolute difference between measured EtAA concentrations and steady state EtAA concentration.

(2) Percent duration without large deviation of  $EtO_2$ :

Percent duration of  $EtO_2$  concentration during steady state maintained within the acceptable limit, which is defined as 5% v/v. This definition is similar to that of the EtAA, except that the acceptable limit is set as 5% v/v.

**NOTE:** The steady state concentration is based on extraction algorithm for both Et Control and Control arms as well as based on the clinician's recorded target values for the Control Arm and the set target values for the Et Control Arm.

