## 6.2 Study Procedures

### 6.2.1 Induction and Intubation Phase

For purposes of this study, induction/intubation phase starts when the Aisys CS machine records FiO2 >80% (pre-oxygenation) with end tidal CO2 breaths detected. During this phase, the subjects from both study groups receive the standard of care from their attending clinicians. This phase ends once maintenance phase begins, the subject is intubated (LMA or endotracheal) and when mechanical ventilation is turned on.

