### 6.2.3 Emergence Phase

This phase starts once the clinician stops administering anesthetic agent and the fresh gas flow rate is > 4 l/min for 5 breaths to begin washing out the inhaled anesthetic agent from the patient in preparation for the subject to regain consciousness. When no additional breaths are detected by the Aisys CS, then the patient is disconnected from the anesthesia machine. This phase ends when the subject is finally disconnected from Aisys CS anesthesia machine.

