## 8. DATA ANALYSIS AND STATISTICS

### 8.1 Statistical Analysis Methods

#### 8.1.1 Sample Size Determination

This study is intended to demonstrate that Et Control is non-inferior to the control device in maintaining end tidal anesthetic agent (EtAA) and end tidal oxygen (EtO2) concentrations.

The primary efficacy endpoint is the weighted average per subject of percent duration of EtAA and EtO2 concentrations maintained within the acceptable range for a subject. The acceptable range is specific for each steady state. For EtAA, the acceptable range is defined as +/- the larger of 5% of the steady state concentration or 0.1% v/v for Iso, 0.2% v/v for Sev, 0.6% v/v for Des; and for EtO2, it is +/- 5% v/v. The duration of each steady state will be used as the weight when calculating the weighted average. For EtAA,

$$\text{PercentDuration} = \frac{\sum_j \sum_i t_{ij} I_{ij}}{\sum_j T_j} \times 100\% \quad \text{where } t_{ij} \text{ is the } i^{\text{th}} \text{ duration of EtAA concentration}$$

maintained within the acceptable limit during the  $j^{\text{th}}$  steady state, and  $T_j$  is the total duration of the  $j^{\text{th}}$  steady state.  $I_{ij}$  is an indicator for whether EtAA is maintained within the acceptable limit of  $i^{\text{th}}$  duration in  $j^{\text{th}}$  steady state, which is

$$I = \begin{cases} 1 & \begin{array}{l} \text{if Desflurane and } \Delta\text{EtAA} \leq \max(0.6\%, 5\%X \text{ steady state EtAA}) \\ \text{if Sevoflurane and } \Delta\text{EtAA} \leq \max(0.2\%, 5\%X \text{ steady state EtAA}) \\ \text{if Isoflurane and } \Delta\text{EtAA} \leq \max(0.1\%, 5\%X \text{ steady state EtAA}) \end{array} \\ 0 & \text{otherwise} \end{cases}$$

$\Delta\text{EtAA}$  is the absolute difference between measured EtAA concentrations and steady state EtAA concentration.

Similar definition is used for EtO2 except that acceptable limit is set as 5% v/v.

From the results of the feasibility study, the average percent duration of EtAA and EtO2 concentrations that exceeded the defined acceptable range for the Control Arm was about 13% and about 18%, respectively. In this study, the non-inferiority margin is set at 5% for both EtAA and EtO2, which is about 1/3 of the performance of the Control Arm, i.e., Et Control will be considered non-inferior to the control device if its performance is no worse than that of the control device by more than 5%.

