So the hypotheses on the primary endpoints are:

$$H_0: \mu_{\text{et}} - \mu_{\text{con}} < -5\% \text{ vs } H_1: \mu_{\text{et}} - \mu_{\text{con}} \geq -5\%$$

**Study Title:** Multi-site Anesthesia randomized controlled Study of End tidal control (Et Control) compared to conventional anesthesia Results (MASTER-Anesthesia Trial)  
**Study No:** 123.07-2015-GE5-0002

GE Healthcare

for both EtAA and EtO2, where  $\mu_{et}$  is the percent duration of Et Control with EtAA and EtO2 maintained within the acceptable range, and  $\mu_{con}$  is the percent duration of control device with EtAA and EtO2 maintained within the acceptable range.

Both null hypotheses have to be rejected for EtAA and EtO2 to conclude non-inferiority. So the alpha is set at 0.025 one-sided with no need for multiplicity adjustment, but the power for each hypothesis is set at 0.95 to have an overall power of 0.9 for the study. And the larger sample size calculated for EtAA and EtO2 will be the size of the study.

The results from the feasibility study on the weighted average of percent duration with EtAA and EtO2 maintained within the acceptable range is listed below. The difference between Et Control and control device is assumed to be 50% less than what was observed, and the larger standard deviation observed is used in sample size calculation using the 2-sample t-test method.

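### The primary endpoints have no scoring window, so steady states before Et Control is on, and agent washout in emergence, count toward the non-inferiority test

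*Combined protocol and SAP*

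**What the plan says.** Section 3.4.1 defines the agent endpoint as "Percent duration of EtAA concentration during steady state maintained within the acceptable limit", averaged over all of a subject's steady states with their durations as weights. EtO2 is handled in the same way with a limit of 5% v/v. Section 8.1.3 repeats the rule and names no phase.

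Appendix 2 defines a steady state for scenario 1. After a setting change, the reading must change by less than 0.2 %v/v per minute for 2 minutes (agent) or by less than 1.5 %v/v per minute for 1 minute (oxygen). The steady state then runs to the next significant setting change, and its own mean becomes the desired concentration. In scenario 2 the reference is the clinician's recorded target (Control) or the set target (Et Control).

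On timing, section 6.1.1 starts the machine log at case start and says that evaluable "data ends when the patient is finally disconnected from the Aisys CS 2 breathing system". It gives no start for evaluable data. It also says: "The investigator will initiate Et Control after the airway is secured (intubation) and mechanical ventilation is initiated". The three phases are defined in section 6.2:

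- Under 6.2.1, the "induction/intubation phase starts when the Aisys CS 2 machine records" an inspired oxygen fraction above 80% with breaths detected. Both groups receive standard care in this phase.
- Under 6.2.2, maintenance starts once ventilation has been on for 10 breaths. A note adds that Et Control is meant to stay in use through emergence.
- Under 6.2.3, emergence starts once the clinician "stops administering anesthetic agent and the fresh gas flow rate is > 4 l/min for 5 breaths".

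Other measures do have windows: agent usage (8.1.4.2), setting interactions (8.1.4.3) and oxygen usage (8.1.9).

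**The concern.** The objective in section 3.3.1 is that Et Control achieves and maintains concentrations no worse than conventional practice. Read as written, the score also contains time that cannot show this.

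- **Before Et Control is on.** A minute of stable, high EtO2 qualifies as a steady state. In the Et Control arm this is fresh-gas performance counted as device performance. Since care is the same in both arms up to that point, randomization makes the expected arm difference zero, whatever the score level. Adding such time pulls the observed difference toward zero, and with a fixed 5-point margin that helps an inferior device to pass.
- **After agent is stopped.** There is no longer an agent level to hold. In scenario 1 the tail can still qualify as a steady state and be compared with its own average. The result then reflects washout kinetics and the fixed limits for each agent. Agent is not a stratification factor.

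Section 8.4 makes the non-inferiority tests the pass criterion, so the window is part of the pass/fail rule.

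**Working it through.** **Step 1: the plan's sample size.** Inputs from section 8.1.1: "the non-inferiority margin is set at 5% for both EtAA and EtO 2"; "So the alpha is set at 0.025 one-sided with no need for multiplicity adjustment"; "the power for each hypothesis is set at 0.95 to have an overall power of 0.9 for the study". Table 8-1 gives EtAA 90 against 87 with SD 16 (difference +3), EtO2 89 against 81 with SD 19 (difference +8), and 15% dropout.

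Normal approximation: n = 2(1.960 + 1.645)² SD² / (5 + difference)².

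- EtAA: 2 × 12.995 × 256 / 64 = 103.96, so 104. The noncentral t gives 105, and 105 / 0.85 = 123.5, so 124.
- EtO2: 2 × 12.995 × 361 / 169 = 55.5, so 56. The noncentral t gives 57, and 57 / 0.85 = 67.1, so 68.

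Both match Table 8-1, so the same model is used below with 105 evaluable subjects per arm.

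**Step 2: dilution.** Let f be the share of a subject's scored time that falls outside maintenance.

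Observed difference = (1 − f) × maintenance difference + f × difference elsewhere.

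For time before Et Control is on, the last term is zero in expectation. A 5-point maintenance deficit then appears as 5(1 − f), and the maintenance deficit that sits exactly on the margin is 5 / (1 − f).

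**Step 3: error rate.** At a true 5-point maintenance deficit the noncentrality is 5f / (SD × √(2/105)). The standard errors are 2.208 (SD 16) and 2.622 (SD 19). The SDs are kept at their Table 8-1 values.

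| f (assumed) | 5-point deficit appears as | Margin acts as | EtAA pass chance | EtO2 pass chance |
|---|---|---|---|---|
| 0 | 5.00 | 5.00 | 2.5% | 2.5% |
| 0.05 | 4.75 | 5.26 | 3.2% | 3.1% |
| 0.10 | 4.50 | 5.56 | 4.1% | 3.8% |

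With all 124 per arm evaluable, the figures at f = 0.05 and 0.10 are 3.3% and 4.3% (EtAA) and 3.2% and 4.0% (EtO2). These are chances per endpoint; the study also needs the other endpoint to pass.

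**Step 4: is 5–10% plausible?** The documents do not give f. Assume 3 to 5 minutes of stable time before Et Control, in 60 to 180 minutes of scored time (60 minutes being the minimum expected case length). Then f runs from 3/180 = 1.7% to 5/60 = 8.3%. At those ends the margin acts as 5.08 and 5.45. So 5% fits a short case, and 10% lies slightly beyond what this assumption gives for pre-device time alone. This applies mainly to EtO2: induction is intravenous, so little agent is likely to be present before maintenance.

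**Step 5: the washout tail under scenario 1.** Illustration: C(t) = C0 × exp(−t/τ) from 1 MAC (1.15, 2.1 and 6.0 %v/v for isoflurane, sevoflurane and desflurane, from the footnote in section 2.1.3). Assume τ of 3, 5 or 8 minutes and a washout of 5, 10 or 15 minutes. The fall rate is C/τ, so the stability rule admits the curve once C is below 0.2τ, that is 0.6 to 1.6 %v/v. Scoring the admitted part against its own mean gives:

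| Agent (absolute limit) | Steady state forms | Time in range when it forms |
|---|---|---|
| Isoflurane (0.1) | 9 of 9 cases | 21–54% |
| Sevoflurane (0.2) | 7 of 9 | 32–86% |
| Desflurane (0.6) | 4 of 9 | 100% |

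The tail's score therefore depends on agent and washout speed and need not be high.

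**The case against.** Several points on the other side are sound.

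- **Only steady-state time is scored.** A reader might infer that the whole machine log counts. It does not: the denominator is the summed duration of steady states, and unstable stretches drop out. This limits f but does not set it to zero.
- **Time outside maintenance is not in range regardless of the device.** That is a tempting inference from the absolute limits, but the documents do not say it, and step 5 contradicts it for isoflurane and often for sevoflurane. The dilution argument for pre-device time does not need it; it needs only equal care in both arms.
- **Emergence is intended Et Control use** (note in 6.2.2). An arm difference there may be a real device effect, so one cannot say that emergence pushes the result toward a pass.
- **Scenario 2 works differently.** The own-mean mechanism is absent, and section 8.3 drops stretches with a missing recorded target. The open window remains, however, and the plan names no reference for the Et Control arm before a target has been set.
- **The margin might scale too.** Section 8.1.1 sets 5% as about one third of Control's out-of-range time (13% and 18%). If the feasibility figures used the same open window, dilution shrinks both benchmark and deficit, and their ratio is unchanged. The documents do not say which window was used. The test itself uses a fixed 5 points.
- **A cut at emergence may differ by arm.** Section 6.2.3 uses fresh gas flow, and section 2.1.6 says Et Control adjusts total flow. This stands, and the fix allows for it.

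**Conclusion.** The point holds in a limited form. The plan states a rule, all steady states up to disconnection, with no phase or mode limit. Applied as written, it credits fresh-gas time before device start to the Et Control arm and, in scenario 1, can score a washout tail as maintenance.

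For pre-device time the direction is clear, toward a non-inferiority pass, and the size is modest. At an assumed 5% or 10% of scored time with no arm difference, the margin acts as 5.26 or 5.56 points, and the one-sided error is about 3.1–3.2% or 3.8–4.1% per endpoint instead of 2.5%. In long cases it is smaller. The figures rest on the Table 8-1 SDs, 105 evaluable subjects per arm, equal care before device start, and a share that the documents do not give. They matter more for EtO2 than for EtAA.

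For washout, neither size nor direction can be fixed. The documents do not support a claim that emergence guarantees in-range time or systematically favors Et Control. The problem there is that the quantity scored is not the one in the objective.

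**What to change.** In sections 3.4.1 and 8.1.3 and Appendix 2, define one scored window for both primary endpoints, the same in both arms and both scenarios:

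- Count only steady states that begin at or after the start of the maintenance phase (6.2.2).
- Stop scoring when agent delivery is stopped, identified by a cut that does not depend on device-driven flow. The flow condition in 6.2.3 should not be used for this analysis cut.
- Report the result over all steady states to disconnection as a sensitivity analysis, and describe emergence performance separately.

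The cost is small: a filter on time stamps derivable from the machine log, plus wording. It needs no new data collection and leaves the planned 248 subjects unchanged. The downsides are slightly less scored time per subject, and that emergence, which is intended Et Control use, is reported outside the primary endpoint.
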